# 6.8 Treatment Exposure and Compliance

Following discharge from the hospital, the Investigator or designee will dispense the appropriate amount of concomitant study treatment per SoC. Drug accountability will be performed to assess compliance at each study visit. The Investigator should promote compliance by instructing the subject to take their study drugs exactly as prescribed and by stating that compliance is necessary for the subject's safety and the validity of the study. The subject should be instructed to contact the Investigator if he/she is unable for any reason to take the study drugs as prescribed.

All drug trough concentrations assessed in this study (siplizumab, TAC) will be measured per the Schedule of Assessments and the Laboratory Manual. For all samples sent for central analysis, the exact time and the date of sampling, together with the exact time and date of the last study medication dose prior to the sampling **must** be accurately recorded on the central laboratory request form (refer to the separate Laboratory Manual). Siplizumab will be measured in serum and TAC will be measured in whole blood.

On the day of a scheduled sampling, the subject will be instructed not to take his/her morning dose of immunosuppressant medications, to record the medication dosage and time of last dose on the day prior to the blood sampling, and to bring all study drugs to the visit so that a dose may be administered upon completion of blood sampling.

#### 6.9 Prohibited Treatment

Immunosuppressants and induction treatment other than those specified in the protocol are NOT allowed after informed consent up to the end of study. If the use of any of these medications or other non-protocol immunosuppressants is discovered prior to randomization/enrollment, the subject must not be randomized and will be recorded as a screen failure. If discovered after randomization/enrollment, no further doses are to be given, and the subject should continue on the randomized/assigned treatment regimen, noting the protocol deviation.

The exception is for the treatment of acute rejection not responding to corticosteroids.

The use of concomitant medications that may influence tacrolimus levels should be avoided, please refer to Appendix 6 and local prescribing information.

## 7 Informed Consent Procedures

Eligible subjects may only be included in the study after providing (witnessed, where required by law or regulation), Institutional Review Board/Independent Ethics Committee (IRB/IEC) approved informed consent.

If applicable, in cases where the subject's representative(s) gives consent (if allowed according to local requirements), the subject must be informed about the study to the extent possible given his/her understanding. If the subject is capable of doing so, he/she must indicate agreement by personally signing and dating the written Informed Consent Form (ICF).

Informed consent must be obtained before conducting any study-specific procedures. The process of obtaining informed consent must be documented in the subject source documents.

ITB-MED will provide to investigators in a separate document a proposed ICF that complies with the International Conference on Harmonization Good Clinical Practice (ICH GCP) guidelines and regulatory requirements and is considered appropriate for this study. Any changes to the proposed consent form suggested by the investigator must be agreed by ITB-MED before submission to the IRB/IEC.

A copy of the approved version of all consent forms must be provided to ITB-MED after IRB/IEC approval.

## 8 Visit Assessments

The Schedule of Assessments is located in Appendix 1 and lists all of the study assessments and when they are to be performed. All data obtained from these assessments must be supported in the subject's source documentation.

While COVID-19 disease remains a risk, efforts to minimize the time a subject spends indoors at the clinic may be considered. These efforts could include use of virtual or telehealth technology, where appropriate, to remotely capture applicable study data (e.g., overall health status, assessment of medication compliance, review of adverse events). The intent is to allow centers to minimize in-person onsite clinic visit activities to those assessments that require the subject to be physically present (e.g., laboratory collections or physical assessments). In the event virtual or telehealth technology is utilized to facilitate data collection, it should be done per institutional practice and local regulations. Detailed documentation of all contact and information collected virtually is to be recorded in the study records.

This protocol defines 7 days to a week and 4 weeks (or 28 days) to a Study Month. For example, Week 2 is considered to start on Day 8 and Study Month 2 is considered to start on Day 29 (Start of Week 5).

Following is a description of study assessments/procedures. For the full Schedule and when to collect for each subject, refer to Appendix 1.

# 8.1 Subject Identification

Each subject is identified in the study by a subject identification number (SID) that is automatically assigned by the EDC system once the subject has signed informed consent, has at least one study assessment or procedure completed, and the relevant data has been entered into the eCRF/EDC by the designated site staff. The SID is retained as the primary identifier for the subject throughout his/her entire participation in the trial. The SID consists of the Site Number (assigned by ITB-MED to the investigative site) with a sequential subject number suffixed to it, so that each subject is numbered uniquely across the entire database.

### 8.2 Screen Failure Assessments

Subjects who sign an ICF and are subsequently found to be ineligible prior to randomization will be considered a screen failure. The reason for screen failure should be recorded on the appropriate eCRF. The demographic information, informed consent, and Inclusion/Exclusion pages must also be completed for screen failure subjects. No other data will be entered into the clinical database for subjects who are screen failures, unless the subject experienced a SAE during the screening phase.

It is permissible to re-screen a subject if s/he fails the initial screening; however, each case must be discussed and agreed with ITB-MED on a case-by-case basis.

# 8.3 Efficacy / Pharmacodynamic Assessments

All blood samples will be taken by either direct venipuncture or an indwelling cannula. Please refer to the Laboratory Manual for a detailed description of central laboratory sample processing, handling, storage, shipment and analytical measures.

### Immunophenotyping

The effect of siplizumab on circulating leukocytes and T-cells will be determined using flow cytometry FACS. Cell subpopulations that will be analyzed may include but are not limited to those bearing one or more of the following cell surface or intracellular markers: CD2, CD3, CD4, CD5, CD8, CD19, CD25, CD27, CD38, CD45RA, CD45RO, CD59, CD127, CD138, CD154, FoxP3 and HLA-DR.

# **Lymphocyte CD2 Receptor Occupancy**

Peripheral CD2 receptor occupancy by siplizumab will be determined by flow cytometry analysis, measuring free or total CD2 receptors on T-cells.

# 8.4 Safety Assessments

# 8.4.1 Physical Examination

A comprehensive physical examination will be conducted at screening, on Day 7 and then at each study visit thereafter. The examination will include a comprehensive assessment of the subject's general appearance, skin, neck (including thyroid), eyes, ears, nose, throat, lungs, heart, abdomen (including spleen and liver), back, lymph nodes, extremities and vasculature. The examination will

also include a thorough neurological evaluation. If indicated, based on medical history and/or symptoms, rectal, external genitalia, breast, and pelvic exams will be performed.

Physical examination findings will be entered in the applicable Physical Examination eCRF. Clinically relevant findings that are present before the subject has had at least one invasive study procedure completed and/or performed must be recorded on the appropriate Medical History eCRF. Significant findings discovered after the start of study procedures, which meet the definition, must be recorded as an adverse event.

## 8.4.2 Vital Signs

Vital signs (radial pulse rate, blood pressure, respiratory rate, and body temperature) will be recorded as indicated in the Schedule of Assessments. Attempts should be made to assess the blood pressure and pulse on the same arm each time of determination and after the subject has rested in the sitting position (may be supine if during hospitalization) for at least five minutes. Body temperature should be measured as per local practice – the same method to be used consistently for all subjects at each site.

# 8.4.3 Height and Weight

Height in centimeters (cm) and body weight (to the nearest 0.1 kilogram [kg]); in indoor clothing, but without shoes will be measured.

Body mass index (BMI) will be calculated using the following formula:

• BMI = Body weight (kg) / [Height (m)]

## 8.4.4 Laboratory Evaluations

Samples for the laboratory tests noted below will be collected at the time points specified in Schedule of Assessments. Refer to the Laboratory Manual for detailed instructions regarding the timing of central laboratory specimen collection along with the handling, processing, storage, and shipping of samples.

In the case where a laboratory assessment that is listed in the inclusion/exclusion criteria is outside of a protocol-specified range at screening and/or at the initial baseline, the assessment may be repeated once prior to randomization. If the repeat value remains outside of protocol-specified ranges, the subject is excluded from the study.

The Investigator must document in the source documents, the clinical considerations and medical relevance of any values outside of the reference range. (i.e., result was/was not clinically significant and/or medically relevant) for all laboratory values.

Clinically relevant deviations of laboratory test results should also be evaluated for criteria defining an AE and reported as such if the criteria are met. Repeated evaluations are mandatory until normalization of the result(s) or until the change is no longer clinically relevant.

Clinically significant abnormalities should be recorded on the relevant section of the Medical History/Current Medical Conditions/AE eCRF page as appropriate.

## 8.4.4.1 Hematology

Hemoglobin, hematocrit, red blood cell (RBC), MCV, MCH, Platelet Count, white blood cell (WBC) and differential count (% and abs).

# 8.4.4.2 Clinical Chemistry

Albumin, total bilirubin, calcium, creatinine, glucose, phosphorus, magnesium, potassium, ALT, AST, ALP, GGT, amylase, sodium, uric acid, and urea/ Blood Urea Nitrogen (BUN) will be measured.

## 8.4.4.3 Lipid Panel

Cholesterol, triglycerides, LDL, HDL will be measured.

## 8.4.4.4 Urine Dipstick

At a minimum, the following parameters will be measured: pH, protein, blood, glucose, nitrites, and leukocytes.

In the event of positive findings, follow-up urinalysis should be performed per local standards.

## 8.4.4.5 Pregnancy

Serum or urine pregnancy testing will be required for females of child-bearing potential, at timepoints as designated in the Schedule of Assessments. A serum or urine pregnancy test must be obtained up to 72 hours prior to time of transplant and the result must be available and negative prior to administration of investigational product.

### 8.4.4.6 Renal Function

Renal function will be assessed by eGFR, using an automated calculation factoring serum creatinine, demographics and the MDRD4 formula.

## 8.4.4.7 Coagulation Studies

Coagulation studies will be performed, including international normalized ratio (INR)/prothrombin time (PT) and activated partial thromboplastin time (aPTT).

#### 8.4.4.8 EBV-DNA PCR

All subjects will have quantitative EBV viral load measured in serum (or whole blood) by a standardized PCR-based method. All measurements will be conducted centrally by a laboratory utilizing World Health Organization EBV international reference standards.

There are currently no consensus guidelines on thresholds for EBV DNAemia or viral load in adult renal transplant recipients, therefore any PCR positive result that is increasing from baseline or a previous assessment will be flagged to the investigator for local follow-up per protocol, including a full physical and neurological exam with careful attention to the liver, spleen, allograft and lymph nodes. In addition, ad hoc abdominal and allograft ultrasound to screen for signs and symptoms of potential PTLD lesions will be conducted.

Suspicion of PTLD in the setting of increasing EBV viral load should be further evaluated as outlined in Section 8.4.5.

#### 8.4.4.9 CMV DNA PCR

All subjects will have quantitative CMV viral load measured by a PCR-based method, preferably calibrated in IU/mL. The CMV titer in blood should be recorded on the applicable eCRF. No specific viral load cutoffs are available to initiate antiviral therapy. However, persistent low-level viremia (<2500 IU) suggests excess immunosuppression or stimulation by other infections or processes (e.g., rejection). If PCR positive, then treatment should be initiated per local practice.

# 8.4.4.10 Donor Specific Antibodies (DSA)

Blood samples for DSAs (antibodies directed against antigens expressed on donor organs) will be collected and evaluated locally.

# 8.4.4.11 Immunogenicity

The presence of anti-siplizumab antibodies will be determined using a bridging ELISA-based assay.

# 8.4.4.12 Viral Testing and Surveillance

All subjects will be screened/monitored for HBV, HCV, HIV, EBV, CMV, and BK virus per local center practice unless more rigorous testing is required for EBV and CMV monitoring, as noted in Section 8.4.4.8 and 8.4.5. Results of these assessments are to be transcribed into the appropriate eCRF pages.

### 8.4.5 EBV-PTLD Surveillance

Clinical manifestations of EBV infection range from asymptomatic infection to clinically significant and potentially life-threatening disease in transplant recipients. EBV infection can be either primary (new infection occurring in an immunologically naïve subject) or secondary due to either reactivation of latent EBV in the transplant recipient under the pressure of immune suppression or reinfection with a new EBV strain. In general, secondary infection tends to be mild or even asymptomatic. Histologic evaluation is important in defining disease status of a subject with suspected PTLD; manifestations can evolve in individual subjects.

The World Health Organization has provided standardized criteria for the pathologic evaluation of lesions associated with EBV in solid organ transplant recipients.

The following signs and symptoms should guide the clinician in assessing the risk of and for EBV-PTLD (Green and Michaels 2013):

### Signs

- Pallor
- Lymphadenopathy
- Subcutaneous nodules

- Tonsillar enlargement or inflammation
- Hepatosplenomegaly
- Focal neurologic signs
- Mass lesions found on imaging obtained for other reasons

## Constitutional and systemic symptoms:

- Unexplained fever or night sweats
- Malaise
- Weight loss and/or anorexia
- Sore throat
- Swollen glands
- Headache or focal neurologic symptoms

## Allograft-specific symptoms:

- Liver: jaundice, abdominal pain
- Intestine: abdominal pain, gastrointestinal bleeding, nausea and vomiting
- Heart/lung: shortness of breath, cough, decreased lung function (lung alone)
- Renal: kidney dysfunction

### Laboratory tests:

• Serial increase in EBV viral load from peripheral blood

The following assessments may be considered as part of the diagnostic work-up for suspected EBV-PTLD (Green and Michaels 2013):

#### Routine:

- CBC, differential, platelets
- Serum electrolytes, calcium, BUN and creatinine
- Liver function tests
- Uric acid
- Lactate dehydrogenase
- Quantitative immunoglobulins
- EBV serologies (anti- Epstein–Barr nuclear antigens (EBNA), viral capsid antigen (VCA) and early antigen (EA)
- EBV viral load from peripheral blood
- Stool: occult bleeding

- Chest radiograph (anteroposterior and lateral)
- CT or PET scan of neck/chest/abdomen/pelvis
- Core needle or excisional biopsy of lesion(s) with flow cytometry of lymphocytes (when possible)
  - EBER, CD20 histochemistry studies of pathologic samples

In select patients, based on signs, symptoms and routine assessments, the following procedures may be considered:

- Bone marrow biopsy
- Bone scan
- Brain CT/MRI
- Gastrointestinal endoscopy
- Lumbar puncture
- Ultrasound assessment of abdomen and allograft

Any diagnostic procedures or additional laboratory assessments that result in the diagnosis of EBV-PTLD must be captured on the relevant eCRFs.

#### Imaging: PTLD Surveillance 8.4.6

When warranted based on physical examination findings and/or EBV surveillance, subjects should have an ultrasound performed of the abdominal cavity and allograft to rule out nodal and/or extranodal EBV-LPD lesions. CT, MRI and/or PET imaging may be considered for staging and monitoring of biopsy confirmed PTLD.

#### 8.4.7 **Renal Biopsy**

Any biopsies performed according to local practice must be recorded. Biopsies will be read by the local pathologist according to local practice and the 2017 Banff criteria (Appendix 7). The results of the biopsy read by the local pathologist will be listed on the applicable eCRF.

Additionally, for all suspected rejection episodes, regardless of initiation of anti-rejection treatment, a renal biopsy must be performed within 48 hrs. The results will be used for subject management for acute rejection.

Please refer to the Laboratory Manual for details on biopsy handling and histology assessments.

#### 8.4.8 **Treated Biopsy Proven Acute Rejection**

Treated biopsy proven acute rejection (tBPAR) is any condition in which the subject receives anti-rejection treatment and is histologically diagnosed as acute rejection according to the 2017 Banff criteria, including borderline rejections, as outlined in Appendix 7.

#### 8.4.9 **Graft Loss**

The allograft will be presumed to be lost on the day the subject starts dialysis and is not able to subsequently be removed from dialysis. If the subject undergoes allograft nephrectomy prior to starting permanent dialysis, then the day of nephrectomy is the day of graft loss. The reason for graft loss will be recorded on the applicable eCRF. Graft loss is considered an SAE and should be reported on the AE eCRF (as serious), and the SAE reported to ITB-MED Safety within 24 hours.

### 8.4.10 Death

In the event of subject death, the SAE leading to death should be reported to ITB-MED Safety within 24 hours.

### 8.5 Pharmacokinetic Assessments

Pharmacokinetics (siplizumab / anti-siplizumab antibodies)

PK samples will be obtained and evaluated in all subjects at all dose levels, as outlined in the Schedule of Assessments. The timing of the PK sample collection may be altered based on emergent data, but the total number of samples and total blood volume collected will not exceed those stated in the Laboratory Manual.

Siplizumab concentrations will be determined by a validated ELISA method; the anticipated Lower Limit of Quantification (LLOQ) is 10 ng/mL and concentrations will be expressed in mass per volume units. Concentrations below the LLOQ will be reported as "zero" and missing data will be labeled as such in the Bioanalytical Data Report.

The following PK parameters will be determined using the actual recorded sampling times and non-compartmental method(s):  $C_{max}$ ,  $T_{max}$ , area under the curve (AUC) last, AUCinf,  $T_{1/2}$ , Vz/F and CL/F from the serum concentration-time data.

The linear trapezoidal rule will be used for (AUC) calculation. Regression analysis of the terminal plasma elimination phase for the determination of  $T_{1/2}$  will include at least 3 data points after  $C_{max}$ . If the adjusted  $R^2$  value of the regression analysis of the terminal phase will be less than 0.75, no values will be reported for  $T_{1/2}$ , AUCinf and CL.

Follow instructions outlined in the Laboratory Manual regarding sample collection, numbering, processing and shipment.

# 8.6 Assessment of Treatment Exposure and Compliance

PK parameters (measures of treatment exposure) will be determined in all subjects treated with study treatment. TAC trough concentrations will be determined locally and recorded on the relevant trough level eCRF. The local trough values will be used to adjust the TAC dosing as needed.

Compliance with the subject's treatment regimen will be assessed by the Investigator and/or designated site personnel at each study visit and info captured in the source and relevant eCRF.

# 8.7 Exploratory Biomarker Assessments

# 9 Study Discontinuation and Completion

### 9.1 Discontinuation

## 9.1.1 Safety Stopping Rules

The following stopping rules based on potential toxicities will serve as the basis for placing enrollment and dose escalation on hold.

Although the stopping criteria do not incorporate an absolute requirement for causality, the potential relationship between an AE(s) and siplizumab will be evaluated carefully on a case-by-case basis between ITB-MED and the Investigator. Following a review of the AE(s), a decision to permanently discontinue enrollment or re-initiate dosing will be made by the DMC. Dose limiting toxicities (DLTs) will be assessed according to the standardized toxicity grading scale, the National Cancer Institute (NCI) CTCAE version 5.0 (NCI 2017).

- One (1) subject death or graft loss within the first month with the exception of technical failures.
- One (1) subject presents with histologically\* confirmed EBV-PTLD.
- One (1) subject with Grade 3 or higher cytokine release syndrome within 24 hours of any siplizumab administration.
- One (1) subject with any Grade 4 toxicity, considered drug related as determined by the Investigator within the first 28 days.

- Two (2) subjects with sustained (>7 days) Grade 3 neutropenia (neutrophil counts 200/mm3 to < 500 to; 0.2 to <0.5 x 10e9/L) considered related to siplizumab.
- Two (2) or more subjects presenting with Grade 3 or higher toxicity considered drug related as determined by the Investigator, including infusion reactions, within 24 hours of any siplizumab administration.
- Three (3) or more subjects per cohort presenting with Grade IIA or higher BPAR (T-cell mediated rejection (TCMR); central pathology) during the first 6 months post-transplant.

\*NOTE: in the case of suspected PTLD lesions where a biopsy is not possible (e.g., CNS symptoms), radiographic and imaging (MRI) studies may be used to stage and assess the disease.

In addition, safety data will be regularly reviewed by ITB-MED and an independent DMC. This regular review of cumulative data includes near real-time assessment of acute rejection (BPAR), graft losses deaths, and key safety endpoints. In the event the acute rejection rate exceeds a clinically relevant threshold set forth in the protocol and DMC charter, or the *a priori* defined stopping rules, enrollment will be suspended to allow for the early termination of any treatment cohort where the benefit/risk of siplizumab is deemed unacceptable.

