### Safety stopping rules:

In addition to the formal interim analyses and escalation data reviews for dosing decision purposes, the following Safety Stopping Rules will be in effect at any timepoint in the study.

Although the stopping criteria do not incorporate an absolute requirement for causality, the potential relationship between an AE(s) and siplizumab will be evaluated carefully on a caseby-case basis between ITB-MED and the Investigator. Following a review of the AE(s), a decision to permanently discontinue enrollment or re-initiate dosing will be made by the DMC. Dose limiting toxicities (DLTs) will be assessed according to the standardized toxicity grading scale, the National Cancer Institute (NCI) CTCAE version 5.0 (NCI 2017):

- One (1) subject death or graft loss within the first month with the exception of technical failures.
- One (1) subject presents with histologically confirmed EBV-PTLD.
- One (1) subject with Grade 3 or higher cytokine release syndrome within 24 hours of any siplizumab administration.
- One (1) subject with any Grade 4 toxicity, considered drug related as determined by the Investigator within the first 28 days.
- Two (2) subjects with sustained (>7 days) Grade 3 neutropenia (neutrophil counts 200/mm3 to < 500 to; 0.2 to <0.5 x 10e9/L) considered related to siplizumab.
- Two (2) or more subjects presenting with Grade 3 or higher toxicity considered related as determined by the Investigator, including infusion reactions, within 24 hours of any siplizumab administration.
- Three (3) or more subjects per cohort presenting with Grade IIA or higher BPAR (T-cell mediated rejection (TCMR); central pathology) during the first 6 months post-transplant.

Following discharge from the hospital, subjects will have study assessments conducted weekly through Week 10 and then monthly from Month 3 through Month 12 or end of study (EOS). All subjects enrolled will be followed for a minimum of 12 months.

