# 16.5 Appendix 5: Guidelines for MMF Dose Reduction

An Investigator may interrupt temporarily or reduce the dosage of MMF if in his/her opinion this is clinically warranted, in response to any causally associated AE (e.g., neutropenia, thrombocytopenia, leucopenia, hyperlipidemia, hypertriglyceridemia or gastrointestinal intolerance). The following guidelines should be followed:

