#### 4.2.3. Safety Stopping Rules

In addition to the formal interim analyses and escalation data reviews for dosing decision purposes, the following Safety Stopping Rules will be in effect at any timepoint in the study. Although the stopping criteria do not incorporate an absolute requirement for causality, the potential relationship between an AE(s) and Sipilizumab will be evaluated carefully on a case-by-case basis between ITB-MED and the Investigator. Following a review of the AE(s), a decision to permanently discontinue enrollment or re-initiate dosing will be made by the DMC. Dose-limiting toxicities (DLTs) will be assessed according to the standardized toxicity grading scale, the National Cancer Institute (NCI) Common Terminology Criteria for Adverse Events (CTCAE) version 5.0 (NCI 2017):

- One (1) subject death or graft loss within the first month with the exception of technical failures.
- One (1) subject presents with histologically confirmed EBV-PTLD.

- One (1) subject with Grade 3 or higher cytokine release syndrome within 24 hours of any Siplizumab administration.
- One (1) subject with any Grade 4 toxicity, considered drug related as determined by the Investigator within the first 28 days.
- Two (2) subjects with sustained (>7 days) Grade 3 neutropenia (neutrophil counts  $200/\text{mm}^3$  to  $<500$  to;  $0.2$  to  $<0.5 \times 10^9/\text{L}$ ) considered related to Siplizumab.
- Two (2) or more subjects presenting with Grade 3 or higher toxicity considered related as determined by the Investigator, including infusion reactions, within 24 hours of any Siplizumab administration.
- Three (3) or more subjects per cohort presenting with Grade IIA or higher BPAR (T-cell mediated rejection [TCMR]; central pathology) during the first 6 months post-transplant.

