##### **10.1.1. Extent of Exposure**

Summary statistics of exposure to study drug will be tabulated by treatment arm. The exposure will be summarized using duration and average dosing. Duration of exposure is defined as last

Confidential

Page 18 of 28

dosing date – first dosing date + 40; e.g. 5 PK half-lives. Exposure by average dose is defined as X/Y, where X is the total dose received and Y is planned number of doses to be given.

The duration (days) of study medication administration will be summarized. This will be calculated by subtracting the date of the last administration of study medication from the date of first administration and then adding the dosing interval for Siplizumab, TAC, MMF or CS. In calculating the duration of treatment, days of temporary interruption of study medication for any reason will be included. Further, the frequency of dose changes (including temporary dose interruption) will be presented by reason for the change.

Average daily doses will be presented by treatment. “Zero” will be used for periods of temporary interruption of study medication for any reason.

The number and percentage of subjects who prematurely discontinued study medication will be summarized by reason for discontinuation.

Study treatment errors, including uses outside of what is foreseen in the protocol, will be summarized. AEs as a result of study treatment error will also be summarized.

Extent of exposure data will be presented in a listing.

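### The sustained-neutropenia stopping rule has a floor of 200/mm3, so after day 28 deeper related counts meet no listed rule while milder ones do

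*Protocol*

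**What the plan says.** Protocol 9.1.1 lists the events that put enrollment and dose escalation on hold. After a review, the DMC decides whether to stop enrollment permanently or resume dosing. Three entries bear on a low neutrophil count:

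- **Sustained neutropenia:** two subjects with "sustained (>7 days) Grade 3 neutropenia (neutrophil counts 200/mm3 to < 500 to; 0.2 to <0.5 x 10e9/L) considered related to siplizumab". The entry has no day limit.
- **Grade 4:** "One (1) subject with any Grade 4 toxicity, considered drug related as determined by the Investigator within the first 28 days".
- **24-hour toxicity:** two or more subjects with "Grade 3 or higher toxicity considered drug related as determined by the Investigator, including infusion reactions, within 24 hours of any siplizumab administration".

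The other entries cover death or graft loss in the first month, EBV-PTLD, cytokine release ("Grade 3 or higher cytokine release syndrome within 24 hours of any siplizumab administration") and Grade IIA or higher rejection in the first 6 months.

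The Synopsis gives the same list and says that "the following Safety Stopping Rules will be in effect at any timepoint in the study". SAP 4.2.3 repeats it, with the neutropenia entry opening "Two (2) subjects with sustained (>7 days) Grade 3 neutropenia (neutrophil counts" and giving the same band. Siplizumab is given on Days 0 and 4 only (Protocol 6.2.6).

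**The concern.** A safety trigger should not switch off as the event gets worse. By writing a neutropenia rule without a day limit, the sponsor has already judged that late, related, sustained neutropenia in two subjects justifies a hold. The wording applies that judgement to counts of 200 to <500/mm3 and leaves out counts below 200/mm3, which are the more dangerous ones. The cytokine-release, 24-hour toxicity and rejection entries are all open at the severe end; this entry is closed.

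At stake is whether a hold follows automatically from two such cases, or depends on someone acting through another route.

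**Working it through.** **The band.** Since 1/mm3 = 10^6/L, 200/mm3 = 0.2 x 10^9/L and 500/mm3 = 0.5 x 10^9/L. The two expressions agree, so the floor is stated twice in matching units.

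**When each rule can apply to a related neutrophil count**

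- 24-hour toxicity rule: doses on Days 0 and 4, so it ends on Day 5.
- Grade 4 rule: ends at day 28, or at 4 + 28 = Day 32 if the 28 days are counted from the second dose.
- Sustained-neutropenia rule: no end date, but only 200 to <500/mm3.

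**Case check.** All cases are related to siplizumab. For onset by day 28, counts below 200/mm3 are taken as Grade 4, as the rule's own band implies. For later onset the grading does not matter, because the Grade 4 rule has lapsed and the numeric band decides.

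| Case | As written | Floor removed |
|---|---|---|
| Two subjects at 350, sustained, onset day 40 | rule met | rule met |
| Two subjects at 150, sustained, onset day 40 | none met | rule met |
| Eight subjects at 150, sustained, onset day 40 | none met | rule met |
| One at 150 and one at 300, sustained, onset day 40 | none met (one counts) | rule met |
| Two subjects, each 5 days at 300 then 5 days at 150, onset day 40 | none met | rule met |
| One subject at 150, onset day 40 | none met | none met |
| One subject at 150, onset day 20 | Grade 4 rule met | Grade 4 rule met |

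In the fifth row each subject has 5 + 5 = 10 days below 500/mm3 but only 5 days inside the band. Conversely, a subject who spends more than 7 days at 200 to <500/mm3 on the way down or during recovery does count as written, whatever the lowest value.

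**When attribution is plausible.** SAP 10.1.1 defines exposure as last dosing date minus "first dosing date + 40; e.g. 5 PK half-lives". With doses on Days 0 and 4 this is 4 - 0 + 40 = 44. Protocol Section 4 aims at about 45 days of T-cell and NK-cell suppression. From the end of the Grade 4 rule to that marker is Days 29 to 44, or 44 - 29 + 1 = 16 days. This supports attribution in that period; it does not predict neutropenia. Protocol 1.1.4.5 describes faster clearance at low concentrations. MMF is a competing cause: Appendix 5 allows its reduction "in response to any causally associated AE (e.g., neutropenia, thrombocytopenia, leucopenia", among other events.

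**The case against.** The strongest reply is that 9.1.1 is not the only protection.

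- **Suspension clause.** Protocol 4.4 says that enrollment will be suspended if safety endpoints pass a threshold set in the protocol and DMC charter. That wording is mandatory. The charter is not among the documents and may contain a neutrophil limit.
- **Escalation review.** Protocol 6.2.8 bars escalation from a dose not considered safe and requires review of all available safety data. The earliest review point is 28 days after the fourth siplizumab subject's Day 4 dose, about Day 32 for that subject.
- **Continuous monitoring.** Protocol 12.7 keeps AE and SAE rates under continuous watch, and 9.1.1 adds regular sponsor and DMC review.

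This stands as far as visibility goes: two deep, prolonged, related cases would very probably be noticed. It does not close the gap in the list. None of these provisions states a neutrophil threshold in the documents, and 12.7 refers back to the 9.1.1 rules for its criteria.

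It can also be said that the floor is a drafting slip, since the Grade 4 entry also lacks an open-ended phrase. That may be so, but an explicit band in two units will be applied as written.

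Finally, the rule holds enrollment and escalation, dosing per subject ends on Day 4, and only one escalation step is planned. A late event in one of the last subjects may leave nothing to hold. That limits the benefit and stands.

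**Conclusion.** The point holds as a narrow defect in the wording that is worth fixing. It requires two or more subjects, attribution to siplizumab, onset after day 28, and no stretch of more than 7 days inside the band. It follows from reading the rules as written and needs no assumed event rate.

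Four stronger readings are tempting, and the documents do not support them:

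- *That only discretion protects subjects after day 28.* Protocol 4.4 contains a mandatory suspension clause whose charter thresholds cannot be seen.
- *That the gap spans the rest of the 12 months in any practical sense.* That is calendar time. On the SAP's exposure marker the period of plausible attribution is about 16 days, although the rule sets no limit and later attribution is not excluded.
- *That any subject falling below 200/mm3 drops out of the rule.* Time spent inside the band still counts.
- *That a number of missed holds can be given.* The documents state neither the rate of related sustained neutropenia nor the share below 200/mm3.

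The practical benefit depends on enrollment, back-filling or an added cohort still being open. SAP 5.1 reports that the formal interim analysis has already been done.

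**What to change.** In Protocol 9.1.1 and the Synopsis, replace the entry with: *two (2) or more subjects with sustained (>7 days) neutrophils <500/mm3 (<0.5 x 10^9/L) considered related to siplizumab*. This removes both the floor and the Grade 3 label. Repeat the wording in SAP 4.2.3 for consistency; the SAP text does not itself control a hold.

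The cost is a written protocol amendment with IRB/IEC approval and, where required, health-authority approval (Protocol 13.4.4). There may be a few more holds, each resting on at least two related sustained cases below 500/mm3. No extra subjects, scheduled visits or assays are needed: hematology already includes an absolute differential (8.4.4.1), and clinically relevant abnormal values must already be re-tested (8.4.4).

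A separate consistency correction, which carries no weight for this point: SAP 4.2.2 back-fills cohorts to 10, while Protocol 3.1 and SAP 4.2.1 say 12. Ten cannot be split 2:1 (10 x 2/3 = 6.67), so it should read 12.
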